6. TREATMENT PROCEDURES

Investigational Product Dosage, Administration, and Schedule

REMD-477 will be manufactured and packaged by a certified contract manufacturing organization (CMO) and distributed using GCP-compliant clinical trial drug distribution procedures. REMD-477 is supplied as single-use glass vials. REMD-477 is formulated with 10mM sodium acetate, pH 5.2, 5% (w/v) sorbitol, 0.004% polysorbate 20 at a protein concentration of 70 mg/mL.

The formulation of placebo is 10 mM sodium acetate, pH 5.2, 5% (w/v) sorbitol, 0.004% polysorbate 20. REMD-477 or vehicle is to be administered SC using 1 mL size insulin syringes.

Approximately 150 subjects (75 in Part A and 75 in Part B) will be randomized in a 1:1:1 fashion into one of three treatment groups (placebo, 35 mg REMD-477, or 70 mg REMD-477).

SC doses of placebo, 35 mg REMD-477, or 70 mg REMD-477 will be administered at the CRU by a qualified staff member on Day 1, followed with repeated weekly doses for an additional 11 weeks. Twelve total weekly SC doses of placebo, 35 mg REMD-477, or 70 mg REMD-477 will be administered at the CRU by a qualified staff member on Days 1, 8, 15, 22, 29, 36, 43, 50, 57, 64, 71, and 78. Each subject will receive his/her study drug SC injections at the same time of the day as administered on Day 1 (+/- 1 hour).

Each dose will be divided into two blinded 0.5 mL volume SC injections administered to the subject's anterior abdominal wall, for a total dose volume of 1 mL. For the 70 mg REMD-477 dose group, subjects will receive two 0.5 mL SC injections of 70 mg/mL REMD-477 on each scheduled day of dosing. For the 35 mg REMD-477 dose group, subjects will receive one 0.5 mL SC injection of 70 mg/mL REMD-477 and one 0.5 mL SC injection of placebo on each scheduled day of dosing. For the placebo dose group, subjects will receive two 0.5 mL SC injections of placebo on each scheduled day of dosing. For each scheduled dose, the two 0.5 mL SC injections should be placed at a distance of 2 cm apart. Alternating (left or right) sites on the subject's anterior abdominal wall and at a distance of at least 2 cm apart will be used for subsequent SC dosing.

The Principal Investigator or a designee must be present during administration.

Documentation of the investigational product or matching placebo administration will be

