noted on the electronic case report form (eCRF) page and in the source documents. The date, dosage and time of administration for dose will be recorded on the respective eCRF page.

The effects of overdose of REMD-477 are not known. All overdose occurrences must be documented, and corresponding AEs recorded on the appropriate eCRF page and in source documents.

The Pharmacy Guide is provided in [Appendix B](#). Details in preparing and administering all study products are included in the Pharmacy Binder provided by REMD Biotherapeutics prior to the start of the study.

Other Protocol-Required Drugs

There are no other protocol-required drugs.

Safety Data Review and Stopping Rules

Safety Review Committee

The Safety Review Committee meeting will be held via teleconference to review available study data and monitor subject safety. The Safety Review Committee will be composed of the Investigator(s) and REMD Biotherapeutics Medical Monitor and Clinical Operations Director. Additional members may be added as needed. The Committee may recommend to continue dosing, to delay dosing, to increase enrollment, to disqualify a subject, or to decrease/increase dose based on emerging safety, PK, and PD data from this current study or the completed phase 1b/2a study (Protocol R477-201) in type 2 diabetic subjects. Final decisions will be determined by the ~9 -12 voting Safety Review Committee members who include the REMD Biotherapeutics medical monitor and clinical operations director, and the 7- 8 Investigators. At least three fourths of the voting Safety Review Committee members must agree to the decision. All available study data including demographics, medical history, concomitant medications, adverse events, ECG, vital signs, and laboratory results will be reviewed. Data to be reviewed may not necessarily be validated and cleaned (data query resolution may be pending).

Data will be reviewed blinded (i.e., treatment assignment will not be revealed) unless unblinding is deemed necessary for the Safety Review Committee. If deemed necessary, unblinding will be performed according to REMD Biotherapeutics standard procedures.

Safety Data Review

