Study recruitment, progress and safety issues will be reviewed by the investigators, research nurse and research coordinators and communicated to the sponsor on a regular basis. The following will be reviewed: 1) subject enrollment, 2) preliminary findings that might affect the risk/benefit ratio or alter the procedures described in the protocol, 3) any clinically-significant out-of-range laboratory value and a course of action, and 4) any adverse or serious adverse events that might result from the research procedures.

The Safety Review Committee will review all available safety and PD data periodically during the study when approximately 33%, 66%, and 100% of the subjects in Part A have received a randomized treatment. After each safety data review, the Safety Review Committee will decide whether or not to continue with subject enrollment and dosing. Decisions to continue enrollment will be documented in the Safety Review Memo. REMD Biotherapeutics will issue a written notification of these decisions to investigators.

Determination of Adverse Event Severity and Relatedness

Adverse events will be coded per current MedDRA. Determination of the severity of adverse events will be consistent with Common Terminology Criteria for Adverse Events (CTCAE) V. 4.03. The relationship of an adverse event to treatment will be determined by the Investigator (see section 9: Reporting Procedures for All Adverse Events).

Dose Stopping Rules

Dosing will be stopped or modified if treatment-related AEs, changes in vital signs, ECG, or clinical laboratory results are observed and these changes pose a significant health risk, in the opinion of the Sponsor, Principal Investigator or Medical Monitor.

Medically significant AEs considered to be related to the investigational product and serious adverse events considered to be related to study procedures will be followed until resolved or considered stable.

A subject may be terminated at any point in time at the discretion of the Sponsor, Principal Investigator or Medical Monitor.

Stopping Rules for an Individual Subject:

At any time during the study, the subject must discontinue study drug treatment, if one of the following events occur:

- An increase of AST and/or ALT (> 3x ULN) are observed in the presence of increased (> 2x ULN) alkaline phosphatase and/or total bilirubin.
- A sustained AST or ALT increase, defined as three consecutive values of AST and/or ALT greater than 5x ULN within a period of 14 days.

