Readings will be made by gently inserting the test strip into the meter, after which the subject will apply a small drop of blood from the finger to the white target area at the end of the test strip. The blood is then drawn into the test strip, at which time the blood ketone value will be displayed on the blood ketone test meter. Additionally, serum ketones and free

fatty acids will be measured during each weekly visit during the treatment period, as outlined in the Schedule of Assessments ([Appendix A](#)).

Quality of Life (QOL) Questionnaire

The Type 1 – Diabetes Distress Scale (T1-DDS) and WHO-5 Well-Being Index scales ([Appendix D](#)) will be provided to the subject at the beginning of the following study visits: Overnight Baseline Visit and Days 85 and 161(EOS) visits.

The T1-DDS is a validated survey instrument that assesses diabetes-related emotional distress and includes 28 items. Thinking back over the past month, the subject will be asked to indicate the degree to which each of the items may have been a problem.

The WHO-5 Well-Being Index scale includes five statements in which the subject will need to rate based on how the subject has been feeling over the last two weeks.

Blood Volume

It is anticipated that subjects enrolled in this study will agree to provide whole blood for safety, PK, and PD assessments during their participation in this study as listed in [Table 7-1](#):

Table 7-1: Total Blood Volume for samples collected prior to Protocol Amendment #1, for subjects participating in Part A

Procedure	Volume per Collection (mL)	Number of Collections	Total Volume (mL)
Safety (chemistry + hematology)	5	9	45
Fasting Plasma Glucose	2	15	30
Fasting Lipid Panel	5	9	45
Serum PK sample collection	4	6	24
Serum FSH levels (women only) ^Φ	5	1	5 ^Φ
HbA1c	6	4	24
Plasma Glucose via YSI	0.75	27	20
MMTT (glucose & insulin)	40	3	120
GLP-1 (active & total), Glucagon, Plasma insulin and C-peptide	4	6	24
Anti-REMD-477 Ab sample collection *	10 (first) / 5	3	20
Exploratory biomarker collection	30	3	90
Serum Ketones & free fatty acids	1.5	15	22.5
TOTAL **			464.5 469.5^Φ

* First collection is 10 mL, subsequent collections are 5 mL.

** Volume to be collected over approximately 238 days.

**Table 7-2: Total Blood Volume for samples collected under Protocol Amendment #1,
 for subjects participating in Part A**

Procedure	Volume per Collection (mL)	Number of Collections	Total Volume (mL)
Safety (chemistry + hematology)	5	9	45

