Fasting Plasma Glucose	2	15	30
Fasting Lipid Panel	5	9	45
Serum PK sample collection	4	6	24
Serum FSH levels (women only) ^Φ	5	1	5 ^Φ
HbA1c	6	4	24
Plasma Glucose via YSI	NA	NA	NA
MMTT (glucose & insulin)	40	2	80
GLP-1 (active & total), Glucagon, Plasma insulin and C-peptide	4	6	24
Anti-REMD-477 Ab sample collection *	10 (first) / 5	3	20
Exploratory biomarker collection	30	3	90
Serum Ketones & free fatty acids	1.5	15	22.5
TOTAL**			404.5 409.5^Φ

* First collection is 10 mL, subsequent collections are 5 mL.

** Volume to be collected over approximately 238 days.

Table 7-3: Total Blood Volume for samples collected under Protocol Amendment #2, for subjects participating in Part B

Procedure	Volume per Collection (mL)	Number of Collections	Total Volume (mL)
Safety (chemistry + hematology)	5	9	45
Fasting Plasma Glucose	2	15	30
Fasting Lipid Panel	5	9	45
Serum PK sample collection	4	6	24
Serum FSH levels (women only) ^Φ	5	1	5 ^Φ
HbA1c	6	5	30
GLP-1 (active & total), Glucagon, Plasma insulin and C-peptide	4	6	24
Anti-REMD-477 Ab sample collection *	10 (first) / 5	3	20
Exploratory biomarker collection	30	3	90
Serum Ketones & free fatty acids	1.5	15	22.5
Liver Injury Biomarkers	10	5	50
TOTAL**			380.5 385.5^Φ

* First collection is 10 mL, subsequent collections are 5 mL.

** Volume to be collected over approximately 224 days.

Laboratory Safety Tests

Blood and urine samples for laboratory safety tests (clinical chemistry, hematology, and urinalysis) will be collected according to the Schedule of Assessments ([Appendix A](#)).

The date and time of blood and urine collection will be recorded in the subject's source documentation. The tests will be analyzed using standard procedures. White blood cell differentials will be reported in absolute counts.

All laboratory tests must be reviewed by the Principal Investigator or qualified designee prior to the subject receiving each dose. Additional safety laboratory assessments may be performed if clinically indicated.

The following analytes will be tested:

Chemistry

Albumin	Blood urea nitrogen (BUN)
Calcium	Chloride
Glucose	Phosphorus
Potassium	Serum creatinine
Magnesium	Sodium
Bicarbonate	Uric acid
Aspartate aminotransferase (AST)	Alanine aminotransferase (ALT)
Cholesterol	Lactate dehydrogenase (LDH)
Alkaline phosphatase (ALP)	Total bilirubin
Total protein	Direct bilirubin
HDL, LDL, Triglycerides	Total globulin

Hematology

Red blood cells (RBC)
Hemoglobin (Hgb)
Hematocrit (Hct)
Mean corpuscular volume (MCV)

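### The compulsory stopping rule for sustained ALT/AST rises depends on repeat tests with no set level or interval, and no ALT/AST is scheduled between Day 57 and Day 85

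*Protocol*

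**What the plan says.** - **The rule.** Protocol Section 6 (Stopping Rules for an Individual Subject) makes discontinuation compulsory for a sustained rise, defined as "three consecutive values of AST and/or ALT greater than 5x ULN within a period of 14 days". A companion rule can act on one draw: ALT or AST above 3x ULN together with ALP or bilirubin above 2x ULN. A third covers treatment-related events of Grade 3 or worse, with a carve-out for ALT/AST increases as already described.
- **Doses and draws.** Dosing is "on Days 1, 8, 15, 22, 29, 36, 43, 50, 57, 64, 71, and 78". ALT and AST belong to the chemistry panel. After the first dose, both Appendix A schedules place chemistry on Days 8, 15, 29, 43, 57, 85 and at end of study. Blood is taken at the other dosing visits as well: serum ketones and free "fatty acids will be measured during each weekly visit during the treatment period".
- **Review and repeats.** Under Laboratory Safety Tests, "All laboratory tests must be reviewed by the Principal Investigator or qualified designee prior to the subject receiving each dose", and "Additional safety laboratory assessments may be performed if clinically indicated". The text on the whole study period (Synopsis and Section 7) adds that clinically significant abnormalities needing monitoring are followed until resolved or stable. Section 6 has "any clinically-significant out-of-range laboratory value and a course of action" reviewed and passed to the sponsor, allows discretionary stopping, and says of the Safety Review Committee: "The Committee may recommend to continue dosing, to delay dosing, to increase enrollment, to disqualify a subject".
- **Reporting.** SAP 10.1.2 keeps unscheduled laboratory readings out of all summaries, except as baseline. SAP 10.4.2 plans tables of maximum ALT and AST above 3x, 5x and 10x ULN and makes no exception. SAP 10.4.4 does bring unscheduled readings into the QTc outlier analysis.

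**The concern.** The rule is compulsory, yet the data it needs are not scheduled. No text sets the ALT/AST level at which a repeat is required, or how soon. The only ALT/AST level that prompts an extra procedure leads to a FibroScan in a Part B subset. A site that retested every 10 days would be within the protocol and would never meet the rule, because its three values would span 20 days.

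The late gap is a separate problem. A pre-dose review can only look at values that exist, and over the last three doses the schedule supplies none. Transaminases are the foreseeable signal for this drug. Section 2 reports that, in the 70 mg cohort of the type 2 study, 7 of 12 patients had ALT rises up to 3x ULN and one had a single 18x value, all without bilirubin or ALP increases. The Dose Selection Rationale expects 10-30x accumulation. A sustained rise that began after the Day 57 draw might first be seen on a scheduled test at Day 85, when dosing is over.

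**Working it through.** **Check on reading the schedule.** Screening, baseline, Days 8, 15, 29, 43, 57, 85 and end of study make 9 draws. Tables 7-1 to 7-3 each give 9 safety collections. The reading reproduces the plan's own count.

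**Can three scheduled values fall within 14 days?** Span = third day minus first day. The window is +/-1 day at dosing visits and +/-2 at Day 85, so the range is the span minus and plus the sum of the two end windows.

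| Run | Span (days) | With windows |
|---|---|---|
| 8, 15, 29 | 29 - 8 = 21 | 19 to 23 |
| 15, 29, 43 | 43 - 15 = 28 | 26 to 30 |
| 29, 43, 57 | 57 - 29 = 28 | 26 to 30 |
| 43, 57, 85 | 85 - 43 = 42 | 39 to 45 |

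The first three runs end during dosing, and none fits in 14 days. The fourth ends after the last dose on Day 78. Runs that start with the baseline draw are left out because that value precedes any drug. In Part B, for example, Day 1 pre-dose, 8 and 15 span 14 days, but the run would need a pre-treatment value above 5x ULN in a subject admitted under a 1.5x ULN screening limit.

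**The late gap.** Day 57 to Day 85: 85 - 57 = 28 days, or 28 +/- (1 + 2) = 25 to 31.

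**Age of the newest scheduled ALT/AST value at each late dose.**

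- Day 64: 64 - 57 = 7 days (5 to 9)
- Day 71: 71 - 57 = 14 days (12 to 16)
- Day 78: 78 - 57 = 21 days (19 to 23)

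Of the 11 dosing days after Day 1, 5 have chemistry (8, 15, 29, 43, 57) and 6 do not (22, 36, 50, 64, 71, 78). On Days 22, 36 and 50 the newest value is 7 days old.

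**Would weekly chemistry alone make the rule work?** Three weekly draws span 14 days nominally, 12 to 16 with +/-1 windows, so not reliably. A timed repeat is needed: if the third value is due 7 days after the first, windows give 5 to 9 days, which is inside 14.

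**The case against.** The strongest reply is that a rule for sustained rises is meant to be met by repeats after a first high value, not by routine draws. That stands. A reader might infer from the spans above that the rule can never fire, and the documents do not support this: the protocol permits extra tests and, in mandatory wording, expects significant abnormalities to be followed. What is missing is only the ALT/AST level and the interval.

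A reader might also infer that isolated rises go unguarded. They do not. Pre-dose review, sponsor oversight, discretionary stopping and the Safety Review Committee all remain, as does the combined ALT/AST and ALP/bilirubin rule, although that rule does not reach the isolated pattern reported in type 2 diabetes. The Grade 3 carve-out could mean all ALT/AST increases or only those covered by the first two rules; the text does not settle it. Part B's liver-injury biomarkers add some protection, but they fall on Days 57 and 85 and leave the same gap.

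Three further inferences go too far:

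- The 18x case does not show the rule failing. It was a single value that fell below ULN with continued dosing, so it would not meet a sustained rule on any schedule.
- The SAP exclusion does not generally hide subjects. Someone whose scheduled value above 5x ULN prompted the repeats is already in the >3x and >5x maximum tables.
- The remark in Section 2 that rises usually occur 4-14 days after administration does not show that particular late doses go unobserved. It is not said to apply afresh after each weekly dose.

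**Conclusion.** The concern holds, with limits, and is worth fixing. The compulsory >5x ULN rule relies wholly on unscheduled repeats (0 of 3 on-treatment scheduled runs fit in 14 days), and their trigger level and timing are left to each investigator. The 28-day interval without scheduled ALT/AST covers the end of dosing and leaves three pre-dose reviews on values up to 21 days old (23 with windows). Protection against isolated rises is weakened, not absent.

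The SAP effect is narrower. It concerns peaks seen only at a repeat, such as a value above 10x after a scheduled value above 5x, and cases first detected at an unscheduled draw. These would appear in the flagged listings but not in the maximum tables.

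The verdict assumes that sites add no chemistry beyond Appendix A unless they judge it indicated. The earlier studies report no sustained rise above 5x ULN, so the number of subjects affected cannot be estimated.

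**What to change.** 1. **Both Appendix A schedules:** add ALT/AST to the blood already drawn on Days 64, 71 and 78. Extending this to every weekly dosing visit is optional.
2. **SAP 10.1.2 and 10.4.2:** state that the maximum post-dose ALT/AST tables (>3x, >5x, >10x ULN) include unscheduled values, as the QTc outlier analysis does. By-timepoint tables can stay on scheduled values.
3. **Protocol Section 6 (stopping rules) and Section 7 (Laboratory Safety Tests):** require any ALT or AST above 5x ULN to be repeated within 2 to 4 days, and again within 7 days of the first value where visit windows allow (5 to 9 at the extremes). The result should be available before the next dose is given.

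**Cost.** A protocol amendment and one SAP sentence. Three assays per subject, at most 3 x 150 = 450; the true number is smaller if some subjects have passed those visits, which is likely because SAP Section 12 mentions a first interim of Part A. At the 5 mL safety-sample volume this is at most 3 x 5 = 15 mL per subject: 15/464.5 = 3.2% to 15/380.5 = 3.9% of planned blood volume. Subjects above 5x ULN need a between-visit draw. Laboratory turnaround is not given, so a dose may have to wait for the result.

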7. STUDY PROCEDURES

The study will include several parts: Screening Period, Lead-In Period, Baseline Visit, a 12 week treatment period, and a 12 week safety follow-up period. During the study, every effort should be made to perform the study procedures as indicated in the Schedule of Assessments ([Appendix A](#)).

All visits, tests, examinations or specimen collections that are not completed must be reported in the source documents and recorded on the appropriate eCRF page.

All post-dose time points are relative to the time of dosing. Time of dosing is designated as time = 0 hour. When multiple procedures are scheduled at the same time point, the ECG takes precedence over blood collection (i.e., PK sampling, safety testing).

Screening Visit:

All experimental procedures will be explained in writing and orally to the subject by the principal investigator, co-investigator, or appropriate research staff. The objectives of the project, all of the requirements for participation, and any possible discomforts and risks will be clearly explained to each subject orally and in writing in lay terms that he/she is able to comprehend. The subject must sign an IRB-approved informed consent form before participating in any aspect of the study. Subjects may be screened up to 42 days prior to initiating the Lead-in Period. If a subject falls outside the 42 day screening window and continues to remain eligible, the screening window may be extended, but the Screening procedures outside the 42 day screening window must be repeated.

A medical examination, including medical history and physical examination, hematology and blood chemistry, urine tests (including urine pregnancy tests for female subjects), a 12-lead ECG, and other screening tests will be performed as specified in the Schedule of Assessments.

Lead-In Period:

The Lead-in Period applies to all subjects and may begin when a subject is judged by an investigator to be eligible, after the initial screening. For subjects participating in Part A, the Lead-In Period may last between 2 and 4 weeks. For subjects participating in Part B, the Lead-in Period may last between 1 and 2 weeks. The subject will be given a DexCom CGM and subjects in Part A will be required to wear it for a minimum duration of two weeks prior to

the **Baseline Visit**, while subjects in Part B will be required to wear it for a minimum duration of 1 week prior to the **Day 1 Visit**. Insulin treatment will continue, and the subject will be given an insulin usage diary. Assessments of daily insulin use (short-acting, long-acting, and infusional, as appropriate) will be recorded over a 14 day period prior to the Baseline Visit for subjects in Part A, or over a 7 day period prior to the Day 1 Visit for subjects in Part B. During the Lead-In Period, subjects will also record their blood glucose levels in a seven-point glucose profile over a single period of three consecutive days prior to the Baseline Visit (subjects in Part A) or the Day 1 visit (subjects in Part B).

Overnight Baseline Visit (OBV) - applies to a subset of subjects in Part A who were enrolled prior to Protocol Amendment #1:

After the Lead-in Period (which includes the completion of the two week CGM period), eligible subjects will be admitted to the CRU around 4:00 pm for a single overnight stay on one of the following study days: Day -8, -7, -6, -5, -4, -3, or -2 relative to the subject's scheduled dosing day (Day 1). The OBV must be performed within 2 to 8 days (check-in to occur between Day -8 to Day -2) prior to administration of study drug.

At the time of admission, data from the DexCom CGM device, the subject's diary capturing insulin use, and the seven-point glucose measurements will be obtained and reviewed. CGM results from the study DexCom device will be downloaded, and typical measures of glycemic control (mean glucose, standard deviation, time in range) will be recorded. CGM results will be unblinded throughout the study.

Additionally, the following baseline assessments will be completed: medical history, physical exam, body weight, urine pregnancy test, urine drug and alcohol test, 12-lead ECG, and vital signs, per the Schedule of Assessments. Safety and PD labs including serum chemistry, hematology, urinalysis, HbA1c, insulin, C-peptide, glucagon, serum ketones, free fatty acids, and GLP-1 will be collected. Fasting plasma glucose samples will be collected on the following morning, prior to the administration of the MMTT and Arginine Challenge Tests. During the 8 hour overnight fast, plasma glucose via YSI will be measured hourly, and subjects will be allowed to receive juice by mouth, in case of hypoglycemia.

For subjects on insulin pumps: Subjects will be admitted to the CRU at approximately 1600 (4:00 pm). A peripheral IV will be placed at this time. They will be given a standard dinner at 1800 (6:00 pm) for which they can bolus as they normally would via their insulin pump for that

particular meal. At approximately 1900 (7:00 pm), the subjects insulin pump will be disconnected and suspended and IV insulin infusion will begin. Blood glucose control will be maintained per [Appendix C](#) to maintain euglycemia in the 90-120 mg/dl range with start rates described in also in [Appendix C](#). The MMTT and arginine challenge will then be performed the next morning at approximately 8:00 am [please note: the insulin infusion will continue until the completion of the both the MMTT and Arginine challenge Test assessments]. After completing the 2 hour MMTT, subjects will be administered an arginine challenge test. During both challenge tests, C-peptide, glucagon, insulin, GLP-1, and glucose concentrations will be measured. Stimulated C-peptide will be measured with the ultra-sensitive C-peptide kit from Mercodia. Upon completion of all tests, subjects may be given additional insulin via SC injection or a bolus of insulin via either IV or insulin pump, at the discretion of the investigator. Additionally, the subject's insulin pump will be restarted immediately after completion of all tests. Subjects will be monitored closely by CGM and YSI as needed and discharged only after blood glucose is < 250mg/dl and relatively stable (not rapidly declining).

For subjects on insulin injections with basal insulin given at night: Subjects can take their last dose of long acting insulin 1 day prior to admission in the evening. They will be admitted and be administered SC or bolus insulin as they would with their rapid acting injection for dinner. Insulin infusion via IV will start at 7:00 pm. No basal insulin injection will be given SC on the night of admission. After all study procedures have been completed the next morning, subjects may receive additional insulin via SC injection or a bolus of insulin via IV, at the discretion of the investigator. At that time they should take half their normal dose of basal insulin SC. They can take the second half at their usual time later that evening. The following day, they can resume their full, normal basal insulin dose.

For subjects on insulin injections with basal insulin given in the morning: Subjects will take their normal AM dose of basal insulin on the morning of the day of admission. They will be admitted and be administered SC or bolus insulin as they would with their rapid acting injection for dinner. IV insulin will be started at 7:00 pm. Of note, given that subjects will have their basal insulin working overnight, they will likely require much less IV insulin, and thus per [Appendix C](#) will be started on a much lower infusion rate. After all study procedures have been completed the next morning, the subject may receive additional insulin either via SC injection or an IV bolus (at the discretion of the investigator), and subjects will take their regular dose of basal insulin. The following day they can resume their dose in the morning as they usually would.

Baseline Visit (BV) - applies to subjects in Part A who are enrolled at the time of Protocol

Amendment #1:

After the Lead-in Period (which includes the completion of the two week CGM period), eligible subjects will return to the CRU after completing an 8 hour overnight fast at home on the morning of one of the following study days: Day -8, -7, -6, -5, -4, -3, -2 or -1 relative to the subject's scheduled dosing day (Day 1). For subjects who are enrolled at the time of this Protocol Amendment, overnight admission to the CRU will not occur.

At the beginning of the visit, data from the DexCom CGM device, the subject's diary capturing insulin use, and the seven-point glucose measurements will be obtained and reviewed. CGM results from the study DexCom device will be downloaded and typical measures of glycemic control (mean glucose, standard deviation, time in range) will be recorded. CGM results will be unblinded throughout the study.

Additionally, the following baseline assessments will be completed: medical history, physical exam, body weight, urine pregnancy test, urine drug and alcohol test, 12-lead ECG, and vital signs, per the Schedule of Assessments. Safety and PD labs, including serum chemistry, hematology, urinalysis, HbA1c, insulin, C-peptide, glucagon, serum ketones, free fatty acids (FFA), and GLP-1 will be collected. Fasting plasma glucose samples will also be collected, prior to the administration of the MMTT. For all subjects, fasting blood glucose should be 80-180 mg/dl. During the overnight fasting at home, subject can drink juice or take glucose tabs if hypoglycemic. No rapid acting insulin should be taken within 4 hours prior of the MMTT. During the MMTT, C-peptide, glucagon, insulin, GLP-1, and glucose concentrations will be measured. Stimulated C-peptide will be measured with the ultra-sensitive C-peptide kit from Mercodia.

For subjects on insulin pumps: The insulin pump will continue until the completion of the MMTT.

For subjects on insulin injections with basal insulin given at night: Subjects can take their last dose of long acting insulin in the evening prior to the Baseline Visit.

For subjects on insulin injections with basal insulin given in the morning: Subjects will take their normal AM dose of basal insulin in the morning a day prior to the Baseline Visit, as well as on the morning of the MMTT.

Upon completion of all tests, subjects may be given additional insulin via SC injection or a bolus of insulin via either IV or insulin pump, at the discretion of the investigator. Subjects will be

monitored closely by CGM as needed and discharged only after blood glucose is < 250 mg/dl and relatively stable (not rapidly declining).

Please Note: Neither the Overnight Baseline Visit (OBV) nor the Baseline Visit (BV) apply to subjects enrolled in Part B.

Randomization and Day 1 Treatment for Subjects Enrolled in Part A: Week 1

On the morning of Day 1, eligible subjects will return to the CRU and will be randomized to placebo or REMD-477 at 35 mg or 70 mg, and undergo pre-dose safety, laboratory, and PD measurements as outlined in the Schedule of Assessments.

After completion of the pre-dose Day 1 tests and procedures, subjects will be administered study drug by SC injection. Upon completion of post-dose procedures, subjects will be discharged from the CRU when the Investigator feels that the subject's condition is stable.

Subjects will also be given the "Week 1" insulin usage diary to record daily insulin use. For Week 1, assessments of daily insulin use will be obtained by taking the average total daily insulin dose (short-acting, long-acting, and infusional as applicable) collected over seven days. To mitigate a potential risk of hypoglycemia, subjects with HbA1C ≤ 8.0% at screening, at the discretion of the investigator, may reduce their total insulin dose by 10-20% on the day of randomization. Hypoglycemia of different magnitudes will be evaluated via CGM. For this study, the primary threshold for hypoglycemia will be set at ≤ 70 mg/dl and second threshold at <54 mg/dL.

Baseline, Randomization and Day 1 Treatment for Subjects Enrolled in Part B: Week 1

After the Lead-in Period (which includes the completion of the one week CGM collection period), eligible subjects will return to the CRU for the Day 1 Visit and will be randomized to placebo or REMD-477 at 35 mg or 70 mg. Prior to being dosed, the subject will undergo all pre-dose safety, laboratory, and PD measurements as outlined in the Schedule of Assessments, as these will serve as the subject's baseline.

After completion of the pre-dose Day 1 tests and procedures, subjects will be administered study drug by SC injection. Upon completion of post-dose procedures, subjects will be discharged from the CRU when the Investigator feels that the subject's condition is stable.

Subjects will also be given the "Week 1" insulin usage diary to record daily insulin use. For

Week 1, assessment of daily insulin use will be obtained by taking the average total daily insulin dose (short-acting, long-acting, and infusional as applicable) collected over seven days (starting on Day 1). For this study, the primary threshold for hypoglycemia will be set at ≤ 70 mg/dL and second threshold at < 54 mg/dL.

For Dose 2 through Dose 12: Week 2 through Week 12

Subjects will return to the CRU on an outpatient basis to receive weekly SC injections of REMD-477 or placebo for a total of 12 injections. Follow-up phone calls by the research staff will occur 3-4 days after Dose 1 and Dose 2 to assess subject insulin use and glucose control and to coach the subject on insulin dosing as needed to minimize hypoglycemia. Safety, PK, and PD assessments will be conducted on an outpatient basis at various time points as described in the Schedule of Assessments. These assessments will include physical exam, body weight, urinary pregnancy test (women), urine drug and alcohol test, 12-lead ECG, vital signs, serum chemistry, hematology, urinalysis HbA1c, insulin, C-peptide, glucagon, GLP-1, and REMD-477 serum concentrations, and fasting glucose (subjects should be instructed to fast overnight for 8 hours prior to collection). For subjects enrolled in Part B, additional safety assessments will include blood collection for liver injury biomarkers at timepoints outlined in the [Schedule of Assessments – Part B](#).

Subjects will be given an insulin usage diary at the beginning of Weeks 2 through 4 to record daily insulin use. For Weeks 2 through 4, assessments of the daily insulin requirements will be obtained by taking the average total daily insulin dose (short-acting, long-acting, and infusional as applicable) collected over seven days.

Subjects will also be given an insulin usage diary at the beginning of Weeks 8 and 12. For these weeks, assessments of daily insulin use will be obtained by taking the average total daily insulin dose (short-acting, long-acting, and infusional as applicable) over a period of three consecutive days within that respective week.

Follow-up and End of Study (EOS): Week 13 through Week 24

Subjects receiving all 12 doses will be followed for 12 weeks after the last dose and will complete study evaluations as described in the Schedule of Assessments.

At Week 13 (1 week after receiving Dose 12) and Week 24 (End of Study Visit), a subset of subjects in Part A enrolled prior to Protocol Amendment #1 will be admitted to the CRU to

complete an MMTT and arginine challenge test, after an overnight fast of at least 8 hours in a similar manner as done at the Overnight Baseline Visit. During the 8 hour overnight fast, plasma glucose via YSI will be measured hourly, and subjects will be allowed to receive juice by mouth, in case of hypoglycemia. During both challenge tests, C-peptide, glucagon, insulin, GLP-1, and glucose concentrations will be measured. Stimulated C-peptide will be measured with the ultra-sensitive C-peptide kit from Mercodia.

For ongoing or newly enrolled subjects participating in Part A at the time of Protocol Amendment #1, overnight admissions to the CRU at Week 13 and Week 24 will not occur. For these visits, subjects will still return to the CRU to complete all the study procedures outlined in the Schedule of Assessments table – however, all assessments for that visit will be performed on a single day (i.e., the Week 13 Visit will be performed on Day 85, and the Week 24 Visit will be performed on Day 162).

For subjects enrolled in Part A:

- **Please Note:** For ongoing or newly enrolled subjects at the time of Protocol Amendment #1, the MMTT will only be administered at the Baseline and Week 13 visits, after the subject completes an 8 hour overnight fast at home (the MMTT is no longer required at Week 24). No Arginine Challenge Tests or YSI assessments will be performed for these subjects.

For subjects enrolled in Part B:

- **Please Note:** Neither the MMTT assessment nor Arginine Challenge Test assessment will be conducted.

Subjects will also be given an insulin usage diary at the beginning of weeks 16 and 20. For these weeks, assessments of the daily insulin requirements will be obtained by taking the average total daily insulin dose (short-acting, long-acting, and infusional as applicable) over a period of three consecutive days within that respective week.

Subjects who early terminate from the study during the 12-week treatment period will be monitored for 12 weeks after the last injection of study drug (REMD-477 or placebo).

Throughout the Study: Day 1 through End of Study

